The Treatment Phase will extend from Cycle 1, Day 1 to Cycle 6, Day 21; or until study drug discontinuation due to either disease progression or unacceptable toxicity; or other reasons whichever occurs first, as listed in Section 3.9. Details of the procedures performed during the Treatment Phase are outlined in the Time and Events Schedules. Patients will be closely monitored for adverse events and other safety evaluations including laboratory investigations, concomitant medications. If disease progression is diagnosed before Cycle 6, Day 21, then the patient will discontinue study drug with completion of the End-of-Treatment Visits on the day of progression, and will enter the Follow-up Phase.

END-OF-TREATMENT VISIT (EOT)

An End-of-Treatment Visit is to be scheduled on Cycle 6, Day 21 of the study drug administration. In a case where patient discontinues the study treatment for any reason listed in Section 3.9 before Cycle 6, Day 21, last visit of the patient will be considered as End-of-treatment visit. Every effort should be made to conduct the telephonic End-of-Study Visit before the patient starts subsequent treatment.

FOLLOW UP PHASE (END-OF-STUDY)

A telephonic follow-up will be conducted 28 days after the EOT Visit. This will be considered as End-of-study visit.

The observation period including the Enrolment Visit and telephonic end-of-study visit will be up to a maximum duration of approximately 23 weeks for each patient.

PATIENT POPULATION

Key eligibility criteria include the patients of either sex who are ≥18 years of age with metastatic EGFR T790M mutation-positive NSCLC, as detected by an appropriate test, who have progressed on or after EGFR TKI therapy by an independent clinical judgment of treating physician based on locally approved prescribing information. Patient with either the history of hypersensitivity to excipients of the study drug or to drugs with a similar chemical structure or class to the study drug OR with pregnant and/or lactating women OR patients participating in any current or future interventional trial will not be enrolled in the current study.

DURATION OF TREATMENT

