Visit No.	1	2-7 (Day 1 of each cycle)	8	202
Study Days	-6 to 0	1-109 (21 day per cycle)	131	28 days post- EOT
Screening/Enrolment visit				
Informed consent ^(b)	Patients r	nust sign the informed conser procedures are p		study-specific
Eligibility Criteria	X			
Demographics/ Review medical history	X			
WHO Performance Status	X	X	X	
General Physical examination	X	Symptom-directed physical	examination only	
Concomitant medication recording	Continuous from time of ICF until 28 days after last osimertinib dose in treatment phase.			
Study Drug Administration				
Osimertinib dosing		The recommended dose is 80 mg osimertinib once a day until disease progression or unacceptable toxicity. Each cycle is of 21 days.		
Disease Evaluations (Disease char	racteristics wil	ll be performed as per routine	clinical practice)	
Baseline Disease Characteristics	X			
Safety Evaluations				
Physical examination	X	Symptom-directed physical examination only		
Vital parameters	X	X	X	
Adverse event monitoring		us from time of ICF until 28 days after last study osimertinib dose		
12-lead ECG	X	X	X	
Hematology & Biochemistry	X	X	X	

Footnotes:

- a. The Screening Phase begins when the first Screening procedure is conducted. Screening tests should be performed within 7 days of Cycle 1 Day 1 except for disease evaluations (performed as routine clinical practice).
- b. Must be signed before first study-related activity.

TABLE OF CONTENTS

PAGE

TITLE	PAGE	1
VERSIO	ON HISTORY	2
PROTO	COL SYNOPSIS	3
TIME A	AND EVENTS SCHEDULE	8
TABLE	OF CONTENTS	9
1.	Introduction	13
1.1	Background and rationale for conducting this study	13
1.2	Rationale for study design, doses and control groups	14
1.3	Benefit/risk and ethical assessment	14
1.4	Study Design	14
2.	Study Objectives	14
3.	Patient Selection, Enrolment, Randomisation, Restrictions, Discontinuation and Withdrawal	15
3.1	Inclusion criteria	15
3.2	Exclusion criteria	15
3.3	Patient enrolment and randomization	15
3.4	Procedures for handling incorrectly enrolled or patients	16
3.5	Methods for assigning treatment groups	16
3.6	Methods for ensuring blinding	16
3.7	Methods for unblinding	16
3.8	Restrictions	16
3.9 3.9.1	Discontinuation from study treatment Procedures for discontinuation of a patient from study drug	
3.10 3.10.1	Criteria for withdrawal	
3.11	Discontinuation of the study	18
4.	Study Plan and Timing of Procedures	19
5.	Study Assessments	20
5.1 5.1.1 5.1.2 5.1.3	Safety assessments Laboratory safety assessments Physical examination	21

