3.9.1 Procedures for discontinuation of a patient from study drug

At any time, patients are free to discontinue study drug or withdraw from the study (i.e., study drug and assessments), without prejudice to further treatment. A patient that decides to discontinue study drug will always be asked about the reason(s) and the presence of any adverse events. If possible, they will be seen and assessed by an Investigator(s). Adverse events will be followed up (See Section 6) and all study drugs should be returned by the patient.

Enrolled patients who discontinue the study prematurely should immediately stop taking study drug and complete the procedures described for End of Treatment Visit, as soon as possible but not later than 7 days after discontinuation of study drug.

If a patient is withdrawn from study, see Section 3.9, 3.10, 3.11.

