Patient participation will include a Screening/Enrolment Phase, a Treatment Phase, and a Follow-up Phase. The Screening Phase will be up to 7 days prior to Cycle 1, Day 1. The Treatment Phase will extend from Cycle 1, Day 1 to Cycle 6, Day 21; or until study drug discontinuation due to either disease progression or unacceptable toxicity; or other reasons whichever occurs first, as listed in Section 3.9. Each cycle of treatment is defined as 21 days of once daily osimertinib treatment. The Follow-up Phase will begin once a patient discontinues study drug or on completion of Treatment Phase, and will continue until 28 days after last dose, death, loss to follow up, consent withdrawal for study participation, or study end, whichever occurs first (see Section 3.9, 3.10, 3.11).

Osimertinib will be provided free of cost by the sponsor to clinical trial patient in the Treatment Phase. The sponsor shall provide the laboratory investigations for safety evaluation including hematology, biochemistry and ECG as mentioned in the Time and Event Schedule to monitor the safety throughout the study period.

Figure 1. Schematic Overview of the Study

SCREENING PHASE (VISIT 0)

Patients, or their legally acceptable representative, will provide written informed consent before any trial-specific procedures are performed. During the Screening Phase, eligibility criteria will be reviewed and a complete clinical evaluation will be performed as specified in the Time and Event Schedule. Screening procedures will be performed within 7 days before Cycle 1, Day 1. All baseline disease characteristics will be captured based evaluation performed as a part of routine clinical practice. The Screening laboratory tests, if any, must be completed within 7 days before Cycle 1, Day 1.

TREATMENT PHASE

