The Treatment Phase will extend from Cycle 1, Day 1 to Cycle 6, Day 21; or until study drug discontinuation due to either disease progression or unacceptable toxicity; or other reasons whichever occurs first, as listed in Section 3.9. Details of the procedures performed during the Treatment Phase are outlined in the Time and Events Schedules. Patients will be closely monitored for adverse events and other safety evaluations including laboratory investigations, concomitant medications. If disease progression is diagnosed before Cycle 6, Day 21, then the patient will discontinue study drug with completion of the End-of-Treatment Visits on the day of progression, and will enter the Follow-up Phase.

END-OF-TREATMENT VISIT (EOT)

An End-of-Treatment Visit is to be scheduled on Cycle 6, Day 21 of the study drug administration. In a case where patient discontinues the study treatment for any reason listed in Section 3.9 before Cycle 6, Day 21, last visit of the patient will be considered as End-of-treatment visit. Every effort should be made to conduct the telephonic End-of-Study Visit before the patient starts subsequent treatment.

FOLLOW UP PHASE (END-OF-STUDY)

A telephonic follow-up will be conducted 28 days after the EOT Visit. This will be considered as End-of-study visit.

The observation period including the Enrolment Visit and telephonic end-of-study visit will be up to a maximum duration of approximately 23 weeks for each patient.

5. Study Assessments

The investigator ensures the accuracy, completeness, and timeliness of the data recorded and of the provision of answers to data queries according to the Clinical Study Agreement.

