## 8.7 Safety Analysis

### 8.7.1 Adverse Events

All adverse events (AEs) will be coded by System Organ Class (SOC) and Preferred Term (PT) according to the Medical Dictionary for Regulatory Activities (MedDRA) Version 23.0. The intensity of adverse events is graded by the National Cancer Institute (NCI) Common Terminology Criteria for Adverse Events (CTCAE) version 4.0 or higher.

*Treatment-emergent adverse events are adverse events with onset during the treatment phase or that are a consequence of a pre-existing condition that has worsened since baseline. All reported adverse events will be*

*included in the analysis. For each adverse event, the percentage of subjects who experience at least 1 occurrence of the given event will be summarized.*

*Any AE occurring before treatment with osimertinib will be included in the data listings but will not be included in the summary tables of AEs. Any AE occurring within 28 days of discontinuation of investigational product (i.e., the last dose of osimertinib) will be included in the AE summaries.*

*Any events in this period that occur after a patient has received further therapy for cancer (following discontinuation of osimertinib) will be flagged in the data listings.*

*Adverse events of special interest (for example interstitial lung disease/pneumonitis-like events; QTc prolongation events) will be summarized separately.*

*Summaries, listings, datasets, or subject narratives may be provided, as appropriate, for those subjects who die, who discontinue treatment due to an adverse event, or who experience a severe or a serious adverse event.*

An overall summary will be provided in terms of count and percentages for:

- AEs
- TEAEs
- Grade 3 and above TEAEs
- Grade 3 and above related TEAEs
- Treatment-related TEAEs
- Treatment-related serious TEAEs
- TEAEs leading to dose change/ interruption/ discontinuation
- Treatment related TEAEs leading to dose change/ interruption/ discontinuation
- Serious TEAEs
- Fatal TEAEs
- Related Fatal TEAEs

Summaries in terms of count and percentages by SOC and PT will be provided for the following:

- TEAEs
- Treatment-Emergent SAEs
- Grade 3 and above TEAEs
- Treatment-related TEAEs
- Grade 3 and above treatment-related TEAEs
- TEAEs leading to dose change/ interruption/ discontinuation
- Adverse Events of special interest

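### The final safety call is timed from the End-of-Treatment visit in some places and from the last dose in others, so early stoppers may not be asked about AEs over the full 28-day window

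*Protocol*

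**What the plan says.** **Timing from the End-of-Treatment (EOT) visit.** For a patient who stops before Cycle 6 Day 21, the Protocol synopsis and Section 4 say the "last visit of the patient will be considered as End-of-treatment visit". They then say: "A telephonic follow-up will be conducted 28 days after the EOT Visit". That call is the End-of-Study visit, and Table 1 uses the same anchor. Both places add: "Every effort should be made to conduct the telephonic End-of-Study Visit before the patient starts subsequent treatment".

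**Timing from the last dose.** The Follow-up Phase (synopsis and Section 4) "will continue until 28 days after last dose, death, loss to follow up", among other end points. The AE monitoring row of Table 1 also stops 28 days after the last study dose. SAP 8.7.1, like Protocol 8.5.1, puts into the AE summaries "Any AE occurring within 28 days of discontinuation of investigational product", and equates discontinuation with the last dose. Both plan to flag events in that period that follow further cancer therapy. SAP 5.2 attaches the End-of-Study label to follow-up ending 28 days after the last dose.

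**Other EOT dates for early stoppers.** Section 3.9 asks for EOT assessments after any early stop. Section 3.9.1 wants the EOT procedures done "as soon as possible but not later than 7 days after discontinuation of study drug". Section 4 and SAP 5.2 put EOT on the day of progression when progression is the reason.

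**Last solicited contact.** Section 6.3.5 has the open AE question asked at each contact up to the final follow-up telephone call.

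**The concern.** The study is about safety only. Its primary outcome (Protocol Section 2) is the number and proportion of patients with AEs, SAEs, AEs of special interest and on-study deaths. The analysis window is fixed by the last dose, while the last occasion on which patients are asked about events is fixed by a visit that, on one reading, precedes the last dose. A second sentence invites the call to be moved earlier still.

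Any shortfall falls only on patients who stop early, including those who stop for toxicity, so it would not be random. SAP 7.3 imputes no missing events, so an event that nobody asks about and nobody volunteers counts as no event. With a safety set of 60, each patient whose only event of a given type is missed in this way lowers that proportion by 1/60 = 1.7 percentage points. The error can only run downwards.

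**Working it through.** **Inputs**
- Treatment visits are on Day 1 of each cycle (Table 1).
- "Each cycle of treatment is defined as 21 days of once daily osimertinib treatment" (Section 4), so Day 1 visits fall on days 1, 22, 43, 64, 85 and 106, and Cycle 6 Day 21 is day 6 × 21 = 126.
- Screening lasts up to 7 days; the call is at EOT + 28 (Section 4).

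**The plan's own figure.** Maximum observation = 7 + 126 + 28 = 161 days = 23.0 weeks, which matches the stated 23 weeks or so. For a patient who completes six cycles with a dose on day 126, EOT and last dose coincide and both anchors give day 154. The conflict concerns early stoppers only.

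**Early stoppers.** Let the last dose fall *k* days after the visit taken as EOT (negative if EOT comes later). Then

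call minus last dose = 28 − *k*.

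| Reading of EOT | *k* | Days from last dose to call |
|---|---|---|
| Last attended Day 1 visit, all visits attended | 0 to 20 | 28 down to 8 |
| Last attended Day 1 visit, one visit also missed | 21 to 41 | 7 after to 13 before the last dose |
| Section 3.9.1, EOT 0 to 7 days after stopping | 0 to −7 | 28 to 35 |
| EOT on the day of progression, last dose that day | 0 | 28 |

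The 8 days needs a last dose on Day 21 of one of cycles 1 to 5 (28 − 20 = 8). In cycle 6 an early stop means a last dose by Day 20, so the minimum is 28 − 19 = 9. For the patient at 8 days, the Section 3.9.1 rule gives a call 20 to 27 days later (28 − 8 and 35 − 8).

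**Table 1 day numbers.** Table 1 shows treatment visits to day 109 and EOT on day 131, which differ from 106 and 126. With those, the worst case is 109 + 28 − 130 = 7 days and the maximum period is 7 + 131 + 28 = 166 days (23.7 weeks). The conclusion does not change.

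**The call before new therapy.** Suppose EOT is on the stopping day and new therapy starts *t* days after the last dose, with *t* below 28. A call made before that start leaves at least 28 − *t* days of the window after the last solicited contact. This holds whichever EOT rule is used. It is also the period in which both documents plan to include and flag events after further therapy.

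**The case against.** The best defence is that the wording about the last visit means the discontinuation visit itself. Section 3.9 asks for EOT assessments after any early stop, Section 3.9.1 sets a 7-day limit, and progression has its own same-day rule. On those rules the call comes at least 28 days after the last dose. AE collection is also defined separately from the call: Table 1, Section 4 and SAP 5.2 carry it to 28 days after the last dose. Volunteered AEs are recorded, and SAEs are collected to the end of the study. The sentence about calling before new treatment asks only for best effort.

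Much of this stands. Where Section 3.9.1 is followed, the EOT anchor causes no shortfall. Three things remain:
- Nothing ranks Section 3.9.1 above the last-visit sentence. Section 3.9.1 has stoppers seen by an investigator only where possible, so a patient who stops and does not return is the one that sentence reaches.
- Collection to 28 days is stated, but no contact is scheduled after the call to carry it out.
- The request to call before new therapy applies under every EOT rule.

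A reader might infer more: that 8 days is typical, that averaging the 8-to-28-day range gives the expected follow-up, or that the cited median progression-free survival gives the number of patients affected. The documents support none of these. The average would require that no early stopper has a discontinuation visit, against Sections 3.9 and 3.9.1. Patients who stop for progression have EOT on the day of progression, so they are largely protected from the last-visit problem; their exposure is the call made before new therapy.

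**Conclusion.** The inconsistency holds. The Protocol and SAP use two anchors for the end of safety follow-up and several EOT dates for early stoppers, with no rule of precedence. Depending on which text a site follows, an early stopper who attended every visit is called between 8 and 35 days after the last dose. The low end assumes the last attended Day 1 visit is EOT and no discontinuation visit takes place. The high end assumes EOT 7 days after stopping.

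Separately, a call made before new therapy can leave part of the 28-day window without solicited contact under any EOT reading.

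It would go too far to say that late AEs and deaths will be selectively under-counted. That is possible, and it would act in one direction. Its size depends on how many patients stop without a discontinuation visit, how many start new therapy within 28 days, and how many events are volunteered. The documents give none of these.

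**What to change.** - In the synopsis, Section 4 and Table 1, time the End-of-Study call at least 28 days after the last dose of study osimertinib, with a stated upper window, regardless of the EOT date.
- Limit the last-visit sentence to saying which assessments are tabulated as EOT, and reconcile it with Sections 3.9 and 3.9.1 and the day-of-progression rule.
- State that a call made before subsequent therapy does not replace the 28-day contact.
- Bring SAP 5.2 into line with the same wording. The AE summary window in SAP 8.7.1 needs no change.

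The cost is Protocol and SAP wording, with some calls made later and a second call for some patients. No clinic visit or laboratory procedure is added. For patients already called under the current wording, the interval from last dose to final contact could be tabulated, since SAP 8.5 and 7.3 already rely on those two dates.

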5.1 Safety assessments

5.1.1 Laboratory safety assessments

Blood sample for laboratory measurement will be performed at local laboratory.

Table 2. Laboratory Safety Variables

Haematology/Haemostasis (whole blood)	Clinical Chemistry (serum or plasma)
B-Haemoglobin (Hb)	S/P-Creatinine
B-Leukocyte count	S/P-Bilirubin, total
B-Leukocyte differential count (absolute count)	S/P-Alkaline phosphatise (ALP)
B-Platelet count	S/P-Aspartate transaminase (AST)
	S/P-Alanine transaminase (ALT)
	S/P-Albumin
	S/P-Potassium
	S/P-Calcium, total
	S/P-Sodium
	S/P-Creatine kinase (CK)

5.1.2 Physical examination

A physical examination will be performed and include an assessment of the following: general appearance, skin, head and neck (including ears, eyes, nose and throat), respiratory, cardiovascular, abdomen, lymph nodes, thyroid, musculo-skeletal (including spine and extremities) and neurological systems.

5.1.3 12-Lead ECG

A 12-lead ECG will be taken (supine position, standard ECG with a recommended paper speed of 50 mm/second covering at least 6 sequential beats) after the patient has been lying down resting for at least 5 minutes. The ECG will be evaluated by the investigator and entered as "Normal" or "Abnormal" in the eCRF. If the ECG is evaluated as "Abnormal" the abnormality should be further specified.

6. Safety Reporting and Medical Management

The Principal Investigator is responsible for ensuring that all staff involved in the study are familiar with the content of this section and is responsible for reporting all SAEs and other AEs.

6.1 Definition of adverse events

An adverse event is the development of an undesirable medical condition or the deterioration of a pre-existing medical condition following or during exposure to a pharmaceutical product, whether or not considered causally related to the product. An undesirable medical condition can be symptoms (e.g., nausea, chest pain), signs (e.g., tachycardia, enlarged liver) or the abnormal results of an investigation (e.g., laboratory findings, electrocardiogram). In clinical studies, an AE can include an undesirable medical condition occurring at any time, including run-in or washout periods, even if no study treatment has been administered.

The term AE is used to include both serious and non-serious AEs.

Appendix A to the Clinical Study Protocol.

6.3 Recording of adverse events

6.3.1 Time period for collection of adverse events

Adverse Events will be collected from patient actually taking the study drug throughout the entire treatment period and during the follow-up period until the end of the study. SAEs will be collected from the time at which informed consent is obtained until the end of the study.

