6.3.5 Adverse events based on signs and symptoms

All AEs spontaneously reported by the patient or care provider or reported in response to the open question from the study personnel: 'Have you had any health problems since the previous visit/you were last asked?', or revealed by observation will be collected and recorded in the eCRF. The question will be put to each patient (or parent/legal guardian) in local language from Visit 2 to the last follow-up telephone contact. When collecting AEs, the recording of diagnoses is preferred (when possible) to recording a list of signs and symptoms. However, if a diagnosis is known and there are other signs or symptoms that are not generally part of the diagnosis, the diagnosis and each sign or symptom will be recorded separately.

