8.5.1 Analysis of the primary variable (s)

Adverse Events

The verbatim terms used in the CRF by investigators to identify adverse events will be coded using the Medical Dictionary for Regulatory Activities (MedDRA) and CTCAE grade and will be listed individually by patient. Treatment-emergent adverse events are adverse events with onset during the treatment phase or that are a consequence of a pre-existing condition that has worsened since baseline. All reported adverse events will be included in the analysis. For each adverse event, the percentage of subjects who experience at least 1 occurrence of the given event will be summarized.

Any AE occurring before treatment with osimertinib will be included in the data listings but will not be included in the summary tables of AEs. Any AE occurring within 28 days of discontinuation of investigational product (ie, the last dose of osimertinib) will be included in the AE summaries.

Any events in this period that occur after a patient has received further therapy for cancer (following discontinuation of osimertinib) will be flagged in the data listings.

Adverse events of special interest (for example interstitial lung disease/pneumonitis-like events; QTc prolongation events]) will be summarized separately.

Summaries, listings, datasets, or subject narratives may be provided, as appropriate, for those subjects who die, who discontinue treatment due to an adverse event, or who experience a severe or a serious adverse event.

Clinical Laboratory Tests

Laboratory data will be summarized by type of laboratory test. Descriptive statistics will be calculated for each laboratory analyte at baseline and for observed values and changes from baseline at each scheduled time point. Changes from baseline results will be presented in pre- versus posttreatment cross-tabulations (with classes for below, within, and above normal ranges). Parameters with predefined National Cancer Institute Common Terminology Criteria for Adverse Events (NCI-CTCAE) toxicity grades will be summarized. Change from baseline to the worst adverse event grade experienced by the subject during the study will be provided as shift tables. A listing of subjects with any laboratory results outside the reference ranges will be provided. A listing of subjects with any markedly abnormal laboratory results will also be provided.

Electrocardiogram (ECG)

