Also for AE, compare the end date to the first dose date. If the AE end date is before the first dose date then the AE should be considered as a medical history. Otherwise, the AE will be considered as TEAE.

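### Table 1 and Protocol Section 6.3.1 give different start points for collecting non-serious AEs, and the closing rule of SAP 7.3, applied as worded, would count stable screening-onset AEs as treatment-emergent

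*Protocol*

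**What the plan says.** **Collection.**
- Protocol Table 1 (Time and Event Schedule) has AE monitoring run "from time of ICF until 28 days after last study osimertinib dose".
- Protocol 6.3.1 states that "Adverse Events will be collected from patient actually taking the study drug throughout the entire treatment period" and on through follow-up. Its next sentence sets a different start for serious events: "SAEs will be collected from the time at which informed consent is obtained until the end of the study".
- Protocol 6.3.5 has the open AE question put to patients "from Visit 2 to the last follow-up telephone contact". In Table 1, Visit 1 is screening and Visit 2 is Day 1 of Cycle 1.
- Protocol 6.1 allows an AE to occur when no study treatment has yet been given.
- Protocol 6.3.3 collects, for each AE, start and stop dates and a single maximum intensity covering the whole course of the event.

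**Analysis.**
- Protocol 8.5.1, repeated in SAP 8.7.1: "Any AE occurring before treatment with osimertinib will be included in the data listings", but kept out of the AE summary tables.
- The same two sections define a TEAE as an event that begins in the treatment phase or that reflects aggravation, relative to baseline, of something already present.
- SAP 7.3 ends by comparing the AE end date with the first dose date. An AE that ended before first dose becomes medical history. "Otherwise, the AE will be considered as TEAE".

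**The concern.** The primary outcome is the incidence of AEs, so the date from which they are collected should have one answer. For non-serious events there are two, and no text in either document reconciles them. Because 6.3.1 sets a consent start for SAEs in the very next sentence, the later start for other AEs looks deliberate rather than a slip.

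Two things are at stake. First, the planned listing of pre-treatment AEs would be incomplete at any site following 6.3.1. Second, some screening-onset symptoms are still present at first dose. Whether these enter the TEAE tables could depend on whether the site recorded them and on which of two SAP rules the programmer applies.

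**Working it through.** **1. The plan's own figures.** Inputs: n = 60 and the nine observed rates in Protocol 8.2 (repeated in SAP 4). With x = 60 × rate, the exact limits are lower = Beta(0.025; x, n − x + 1) and upper = Beta(0.975; x + 1, n − x). At 10%, x = 6 and the limits are 3.8% and 20.5%, as printed. All nine rows reproduce to one decimal; the 1% and 2% rows need x = 0.6 and 1.2. The AE start point does not enter this calculation.

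**2. Length of the disputed window.** Screening is at most 7 days, treatment is 6 × 21 = 126 days, and follow-up is 28 days. The total is 7 + 126 + 28 = 161 days = 23 weeks, which matches the stated maximum. The disputed part is at most 7/161 = 4.3% of it.

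**3. Four kinds of event traced through the rules.**

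| Event | Recorded under Table 1? | Recorded as an AE under 6.3.1? | Protocol 8.5.1 / SAP 8.7.1 | SAP 7.3 closing rule as worded |
|---|---|---|---|---|
| Serious, onset in screening | Yes | Yes | No conflict over collection | No conflict over collection |
| Non-serious, onset in screening, over before first dose | Yes | No | Listed, not summarised | Medical history |
| Non-serious, onset in screening, ongoing at first dose, stable | Yes | Unclear; may be omitted or appear only as medical history | Listed, not a TEAE | TEAE |
| Non-serious, onset in screening, worsens after first dose | Yes | Unclear; may be entered as new on drug | TEAE through worsening | TEAE |

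The third row carries the contradiction: the SAP gives two answers for the same event. The fourth row has a different problem. With one maximum intensity for the whole course and no grade at first dose, the variables listed in 6.3.3 cannot separate it from the third row.

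**4. Size per patient.** One patient whose only qualifying event is of this kind moves a term-level rate by 1/60 = 1.7 points. The documents give no count, so k below is an assumption, and all k patients are placed on one preferred term that starts from 6/60:

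| k | Rate | Exact 95% CI |
|---|---|---|
| 0 | 10.0% | 3.8 to 20.5 |
| 1 | 7/60 = 11.7% | 4.8 to 22.6 |
| 3 | 9/60 = 15.0% | 7.1 to 26.6 |
| 6 | 12/60 = 20.0% | 10.8 to 32.3 |

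Spread over several terms, the movement in any one of them would be smaller.

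**The case against.** The strongest reply is that the summaries are already protected. The SAP 7.3 sentence closes the section on missing data, directly after the case where a start date cannot be imputed, so it may be meant only for AEs without a usable start date. For an AE with a known screening onset, SAP 8.7.1 would then govern and a stable event would be listed only. This is a fair reading, perhaps the natural one. It is not what the sentence says, however: nothing in it limits it to missing dates. The effect on the summaries is therefore conditional on the literal reading.

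Other points also stand and limit the concern:
- A reader might infer that 6.3.5 supports 6.3.1 because the AE question starts at Visit 2. It does not clearly do so. On the Table 1 numbering, Visit 2 is Cycle 1 Day 1, and the question looks back to the previous visit, which covers screening. (The narrative headings label screening Visit 0, but Table 1 has the only full numbering.) What is missing is that the question be asked before dosing.
- A reader might infer that no pre-dose record exists. Screening takes medical history, physical examination, vital signs, ECG, laboratory tests and performance status. This is a partial substitute, although no text directs screening-onset symptoms there.
- A reader might infer that sites will differ, or that the primary numerator certainly depends on how each site reads the protocol. The CRF, the Investigator Instructions Manual and site training may settle the start point, and they are not in the documents. Only *may differ* is supported.
- A reader might assume that several patients are affected because this population has progressing disease. The documents give no such rate, and Protocol 6.3.7 excludes events unequivocally due to progression from AE reporting.
- The pre-treatment listing is not empty under 6.3.1, because SAEs are collected from consent.

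**Conclusion.** The contradiction between Table 1 and 6.3.1 is real, unresolved and confined to non-serious AEs. Its certain consequence is that the planned pre-treatment listing presupposes data that 6.3.1 does not collect. Its possible consequence is a TEAE count that depends on site practice. That requires three things: sites read the start point differently, the symptom begins in the screening window and is still present at first dose, and SAP 7.3 is applied as worded. Each such patient is worth 1.7 points on a term-level rate; how many there would be cannot be derived from the documents. This is a minor point that is cheap to correct. It leaves the sample size, the confidence interval table and the collection of serious events as they are.

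**What to change.** 1. Give Table 1 and Section 6.3.1 one start point for all AEs. Consent is the consistent choice, since Table 1 uses it and the pre-treatment listing presupposes it.
2. State in 6.3.5 that the Visit 2 question is asked before the first dose.
3. Limit the closing rule of SAP 7.3 to AEs whose onset cannot be placed before or after first dose. For all others apply the SAP 8.7.1 definition, so that a screening-onset AE is treatment-emergent only if it worsens after first dose.
4. For AEs ongoing at first dose, record the grade at that time, so that worsening can be determined from the data.

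The cost is wording in the protocol and SAP, one data field, and a few extra pre-dose entries.
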